			arrhythmia, then the simulator will be turned off. If this resolves the arrhythmia, then it will be noted that the device likely caused the arrhythmia. If the arrhythmia persists despite the device being turned off, then it is unlikely that the device is the cause of the arrhythmia. If there is suspicion that the lead itself, even while turned off, is responsible for an arrhythmia, then the lead will be removed.
Pneumothorax	Rare	Mild to moderate	It is unlikely that a patient will have a pneumothorax after lead removal. To mitigate this risk, the lead will be removed prior to chest tube removal. Treatment may range from nonoperative management to chest tube placement.

All AEs will be captured via electronic data capture (EDC) system.

Expected Benefits

If the device works the way we expect it to, then the patient should experience pain relief and potentially some paresthesia in the distribution of the intercostal nerves affected. Effective pain control will allow the patient to mobilize earlier in the hospital stay and perform pulmonary toilet functions more effectively without the side effects of systemic opioids or epidurals.

Medical Monitor

To ensure consistent and accurate AE reporting and classification, an independent medical monitor will be established. The medical monitor will assess all AEs captured by the study coordinator(s).

Monitoring

Study monitoring will be performed by experienced and appropriately trained personnel appointed by the sponsor-investigator to ensure that the investigation is conducted accordance with the FDA IDE regulations. Monitoring will be conducted by the independent monitor in CCF HVI Research Department.

HVI (Heart and Vascular Institute) Research Department
Cleveland Clinic Foundation
[name]
[name]

On-site monitoring will occur at regular intervals throughout the duration of the trial, and monitor visit with summary of findings will be outlined in monitoring report.

Monitoring activities will include:

- Study Initiation visit
- Review of training and delegation of authority log
- Review of FDA/IRB approval letters and correspondences
- Review of informed consent to ensure:
 - That the subject signed and dated the informed consent form for him/herself
 - A valid and effective version (reviewed and approved by the IRB) of the consent form was used
 - That the informed consent process was appropriately documented
- Confirmation that the study staff is conducting the study in compliance with the protocol approved by the IRB.
- Source Document Verification (i.e., review all subjects' charts for: study eligibility, primary and secondary endpoints data, and that the protocol specific source documents are on file)
- Ensuring the data reported on the eCRF is consistent with the source documentation
- Review of outstanding queries on the eCRF
- Review of all subject research records to ensure the following:
 - All AEs and SAEs have been reported including any abnormal exam findings determined to be clinically significant;
 - AEs have been reviewed, attribution has been assigned and signed by investigator in a timely manner;
 - EAEs and SAEs have been submitted to the IRB and FDA per IRB/FDA reporting criteria; and
 - All deaths have been reported appropriately
- Ensuring any protocol deviation that meets reporting requirements has been reported to the IRB as well as reported in eCRF
- Ensuring investigational products have been properly handled
- Verification of device used
- Study termination/closure visit

IRB

The protocol shall be evaluated and approved by the Institutional Review Board at the Cleveland Clinic Foundation prior to proceeding with the study.

Institutional Review Board
[name] – IRB Chairman
Cleveland Clinic Foundation
[name]
[name]
[contact]

Investigator Agreement

[name], as a study Sponsor and P.I. will certify all participating investigators will sign the investigator agreement and no investigator will be added until the investigator agreement is signed in accordance with 21 CFR 812.29(b)(5).

Investigator responsibilities include, but not limited to:

- Conducting the study in accordance with the investigational plan, signed agreement and applicable regulations protecting the rights and safety of study subjects
- Informing all subjects that the device being utilized is for investigational purposes, and ensuring that the requirements relating to obtaining informed consent and IRB approval are met
- Ensuring that IRB approval is secured prior to starting the study and ensuring continuing review and approval as required throughout the investigation
- Ensuring and supervising all associates, colleagues, and employees assisting the conduct of the study are informed about their obligations, are adequately qualified and trained, and meet their commitments
- Maintaining adequate and accurate records and ensuring those records are available for inspection at any time
- Ensuring that conducting the study does not give rise to conflict of interest
- Controlling of all investigational devices

Device Charges

The device will be charged at the same amount charged by the manufacturers of the devices to the hospital. The devices that are used as part of their clinical care are billed to the subject and/or his/her medical insurance.

Manufacturing Information

The **Medtronic Intellis Spinal Cord Stimulation (SCS)** is manufactured, sterilized and packaged by Medtronic. We will not be tampering or adjusting the packaging in any way.

Labeling

Sample Label:

Manufacturer
Medtronic, Inc.
[name],
[name],
USA
www.medtronic.com
[contact]
[contact]

Authorized Representative EC REP

in the European Community
Medtronic B.V.
[name],
[name],
The Netherlands
[contact]
[contact]

Europe/Africa/Middle East Headquarters
Medtronic International Trading Sàrl
[name],
[name]
[name],
Switzerland
www.medtronic.eu
[contact]
[contact]

Asia-Pacific
Medtronic International Ltd.
[name],
[name],
Kowloon,
Hong Kong
[contact]
[contact]

Contacts for specific countries are listed inside this cover.

© Medtronic, Inc. 2016
All Rights Reserved

M954166A029 Rev A

Reports

Deviation from the Investigational Plan: The sponsor-investigator will notify the reviewing IRB and FDA of any deviation from the investigational plan to protect the life or physical well-being of a subject in an emergency. The notice will be provided as soon as possible but no later than 5 working days after the emergency occurred. If the change or deviation may affect the scientific soundness of the investigational plan or the rights, safety or welfare of the subject, the sponsor will obtain prior IRB and FDA approval for deviation by submitting an IDE supplement.

UADE: The sponsor-investigator will report the results of an evaluation of an unanticipated adverse device effect to FDA and IRB within 10 working days after the sponsor-investigator first receives notice of the device adverse effect.

Withdrawal of IRB approval: The sponsor-investigator will notify FDA of the withdrawal of IRB approval or any part of the investigation within 5 working days of receipt of withdrawal of approval.

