The investigator will review the patient's history, physical examination, and radiographic studies prior to obtaining informed consent. An IRB approved informed consent form will be obtained from the patient after the purposes of the study, the risks, expected discomforts, and potential benefits have been explained. Because of the need for emergency or urgent operations, the informed consent form may be signed by the patient or by a family member / proxy. Copies of the informed consent will be included in the study records. Another copy will be given to the patient for their records.

Primary Outcome Measures

Primary outcome:

- a. Pain as measured by the visual analog scale
- b. Freedom from bleeding, infection, pneumothorax, arrhythmias

Secondary Outcome Measures

Secondary outcome:

- a. Morphine equivalents taken (both IV and PO) during the inpatient period
- b. Number of narcotics taken post discharge
- c. Pain control as measured by the McGill pain questionnaire.

Hypothesis Testing

This is not a hypothesis driven study. Descriptive summary statistics will be presented for all data points.

Data Collection and Analysis

The data will be collected in a 21CFR part 11 compliant database, REDCap Cloud. No statistical analysis beyond counts and frequencies will be required. The results of this study will be described in a case report format.

Pre-Procedure Screening:

History and physical will be performed to ensure that the subjects meet the inclusion criteria and do not meet any of the exclusion criteria of the study. Women of child-bearing potential, the pregnancy test will be performed prior to the procedure.

Subjects will be asked to answer Mc Gill Pain Questionnaire as a baseline assessment.

Inpatient Days:

Visual analog pain assessment and morphine equivalence will be collected. Daily chest X-ray will be taken and findings will be collected until discharge.

Follow-up:

Subject will return at 2 weeks, 1 month, and at 3 months for pain assessment. If subjects are unable to return, a phone visit will be performed to collect pain assessment and AE assessment.

Follow-up Schedule Table:

Procedures	Screening	Intraoperative	POD 0	POD 1 to Day of Discharge	First outpatient postoperative visit (POD 7 -14)	1 month (POD 21 – 31)	3 months (POD 45 – 90)
McGill Pain Questionnaire	X				X	X	X
Peripheral nerve stimulator placement		X					
Peripheral nerve stimulator activation			X	X			
Peripheral nerve stimulator removal				X			

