Visual Analog Scale Pain assessment			X	X	X	X	X
Chest X-ray			X	X (daily until dc)			
Number of Narcotics Taken			X	X	X	X	X
Assessment of AE		X	X	X	X	X	X

Subject Withdrawal from the Study

A subject may withdraw from the study at any time and should notify the investigator in this event. The investigator may also withdraw the subject from the clinical study at any time based on his medical judgment.

Subject Lost to Follow-up

A subject will be considered lost to follow-up and terminated from the study once they have missed two consecutive appointments without contacts and three attempted contacts are unanswered (it must include a contact with certified letter).

Risk Assessment and Adverse Events

Definition of Adverse Events (AE):

An adverse event is an untoward medical occurrence or exacerbation of an existing medical condition subsequent to the experimental therapy. For this study, adverse events are rated in the following ways:

- Anticipated (anticipated, not anticipated)
- Device and procedure relationships (unrelated, possibly related, or related)

Adverse events will be categorized as either serious or non-serious. A Serious Adverse Event (SAE) is an event that meets at least one of the following:

- Is fatal
- Is life-threatening
- Results in persistent or significant disability/incapacity
- Results in permanent impairment of a body function or permanent damage to a body structure
- Results in hospitalization or prolongs a hospitalization
- Necessitates medical or surgical intervention to preclude permanent impairment of a body function or permanent damage to a body structure

Definition of an Unanticipated Adverse Device Effect (UADE) :

Any serious adverse effect on health or safety or any life-threatening problem or death caused by, or associated with, a device, if that effect, problem, or death was not previously identified in nature, severity, or degree of incidence in the investigational plan or application (including a supplementary application), or any other unanticipated serious problem associated with the device that relates to the rights, safety, or welfare of subjects.

Risks and Risk Mitigations Strategy:

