The purpose of this study is to assess the safety of an electrical stimulation lead in the thoracic cavity. Summary of some of the known risks is identified below; however, there may be risks that are not known or unforeseen at this time. The severity of any particular event may vary depending on the subject's pre-existing conditions or comorbidities. AEs will be collected and classified as device-related, procedure-related or unrelated; events that are related to pre-existing condition are not considered as AEs.

Adverse events associated with the application of this procedure may include, but are not limited to, the following (the severity of any particular event may vary depending on the patient's pre-existing conditions or comorbidity):

Possible AE	Likelihood	Severity	Risk Mitigation Strategy
Discomfort	Less likely	Mild	Very little discomfort is expected. Subjects will have traditional pain

			management methods available to them as well.
Bleeding	Rare	Mild to moderate	
It is unlikely that this device will cause bleeding.
 
If there is bleeding related to the device, then the treatment may range from watchful waiting to blood transfusion and to reoperation.

Infection	Rare	Mild to moderate	
It is unlikely that this device will cause infection.
 
If there is infection related to the device, then the device will be removed. The treatment may range from intravenous antibiotics to reoperation.

Mechanical failure of the lead (lead displacement, lead fracture, wire fracture)	Rare	Mild to moderate	
It is unlikely that this device will have mechanical failure.
 
If there is lead/wire fracture then this would require reoperation. If leads are displaced then the treatment can range from watchful waiting to device removal.

Device malfunction	Rare	Mild	
It is unlikely that the device will malfunction.
 
If the device is not functional, then a new stimulator will be attached to the stimulator leads. If there is not a functional stimulator available, then the leads will be removed.

Arrhythmia	Rare	Mild to moderate	
It is unlikely that there will be arrhythmias caused by the electrical leads. The patients will be attached to the cardiac monitors during the postoperative stay, as per standard care. If the patient develops an

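### A pre-existing condition that worsens after the procedure is an adverse event under the protocol's definition but not under its risk section, and nothing says which rule governs

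*Combined protocol and SAP*

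**What the plan says.** The section Risk Assessment and Adverse Events contains both rules.

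- Under Definition of Adverse Events: "An adverse event is an untoward medical occurrence or exacerbation of an existing medical condition subsequent to the experimental therapy". Events are then rated for their relationship to device and procedure, and unrelated is one of the permitted ratings. The same subsection adds: "Adverse events will be categorized as either serious or non-serious".
- Under Risks and Risk Mitigations Strategy: "AEs will be collected and classified as device-related, procedure-related or unrelated", followed in the same sentence by the statement that "events that are related to pre-existing condition are not considered as AEs".

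Three other places depend on what counts as an adverse event. The Medical Monitor section has the independent monitor assess the events that coordinators have captured. The Monitoring checklist verifies that "EAEs and SAEs have been submitted to the IRB and FDA per IRB/FDA reporting criteria". Primary outcome (b) is "Freedom from bleeding, infection, pneumothorax, arrhythmias", with no restriction by cause and no statement of the record from which it is compiled.

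**The concern.** Two people following this protocol could treat the same post-procedure worsening differently: one enters an adverse event, the other enters nothing. The exclusion acts at capture, so the decision to leave an event out would not reach the medical monitor. The study is unblinded, at one center, and run by a sponsor-investigator, which makes that independent look more valuable.

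Serious adverse events are a category of adverse event. A serious worsening that is not entered as an adverse event can therefore also miss seriousness classification and the submission to the IRB and FDA that monitors check.

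Safety of the lead in the chest is a stated purpose of the study, and the planned output is counts and frequencies. The rule for what enters the count has to be single. If outcome (b) is drawn from adverse event records, any loss would also make the device look safer, including in the progress report due after the first 5 subjects' first follow-up visit.

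**Working it through.** **1. Apply each rule to the same event.** Take an existing condition that worsens after the lead is placed.

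| Rule | Is it an adverse event? |
|---|---|
| Definition of Adverse Events | Yes: worsening is named expressly |
| Risks and Risk Mitigations Strategy | No: the event is related to a pre-existing condition, and worsening is not excepted |

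**2. Look for text that ranks or reconciles them.** Pre-existing conditions are mentioned twice more in the risk section, both times about how severe an event may be. The Medical Monitor and Monitoring sections deal with events already captured or reported. Nothing gives either rule precedence.

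**3. Test the milder readings.**
- *The clause only separates out events not caused by the device.* This does not fit. Both subsections already have an unrelated class of adverse event, so the clause removes events where that class would have labelled them.
- *The clause only excludes the unchanged baseline condition.* The text does not say this. It would also be unnecessary, because an unchanged condition is neither a new occurrence nor a worsening and so falls outside the definition already.

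**4. Trace the route to outcome (b).** In the Follow-up Schedule Table, "Assessment of AE" runs from the operation to 3 months. The chest X-ray row ends at discharge; the remaining rows concern pain, narcotic use and the stimulator itself. After discharge, the adverse event row is the only scheduled one that can pick up any of the four components. In hospital it is the only row that generally covers bleeding, infection and arrhythmia. Compiling (b) from adverse event records is therefore plausible, but it is an inference.

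**5. A worked case.** The exclusion criteria bar active cardiac implants but not a history of arrhythmia without one. Suppose such an arrhythmia worsens. Inpatient cardiac monitoring would detect it. If it continues with the stimulator off, the risk table regards the device as an unlikely cause, though it also allows that the lead itself might be responsible. The definition would have the event recorded and reviewed; the risk section would allow it to be omitted.

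**6. Scale.** The plan gives no figure to reproduce. Assume (b) is compiled from adverse event records, scored as one composite per subject, and that the dropped event is the subject's only one.
- All 10 subjects: 1/10 = 10 percentage points per dropped subject.
- Early report, if its denominator is exactly 5: 1/5 = 20 percentage points.
- No such event: 0.

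As an event frequency, 0/10 is 0% (exact 95% interval 0 to 30.8%), and 1/10 is 10% (0.3% to 44.5%).

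The protocol's background quotes infection in 3.6% to 17.9% of implantable stimulator patients. Applied to 10 subjects, that is 10 × 0.036 = 0.36 to 10 × 0.179 = 1.79 infected. This is not the quantity needed: it describes device complications, the protocol expects a lower risk here, and the share that would be put down to a pre-existing condition is unknown. It carries no weight below.

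**The case against.** The best defence is that the clause sits in the introduction to a risk summary while the definition sits under its own heading, so a sensible reader would follow the definition and take the clause to mean the underlying disease in its natural course. That may be the intent, but it is not written.

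The safeguards are real:
- Chest X-ray findings are collected daily to discharge, with a film after lead removal.
- Patients are on cardiac monitors in hospital.
- Patients with infection, immunocompromise or elevated infection or bleeding risk are excluded.
- Monitors verify endpoint data against charts and check deaths and clinically significant exam findings.
- Unanticipated adverse device effects have their own definition and reporting route.
- Results will be presented as case reports, so a single tally matters less than in a summary-only report.

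These improve detection but do not settle classification. Monitors check compliance with a protocol that gives two answers. The unanticipated-effect route requires an association with the device and something unanticipated, whereas all four components of (b) are already listed as known risks.

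Three points on the other side stand. The effect on (b) is conditional. The 10- and 20-point steps rest on assumptions about a composite and a denominator that the protocol does not state. The study is descriptive with no success threshold, so no formal decision would change.

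**Conclusion.** The concern holds, and the text is wrong as written: a stated rule contradicts the protocol's own definition. Confidence in the contradiction is high because it rests on the wording alone.

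The consequence that does not depend on how (b) is compiled is possible loss of worsenings from the adverse event and serious adverse event record, and from medical monitor review. An effect on (b) requires that it be drawn from those records; under the composite assumption it would be 10 points per affected subject among 10, always in the favourable direction. The number of such events cannot be estimated from the documents and may be zero. This should be fixed, but it does not invalidate the study.

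**What to change.** 1. Delete the clause on pre-existing conditions from Risks and Risk Mitigations Strategy and let the definition govern. It already leaves out an unchanged baseline condition.
2. Record every new or worsened event as an adverse event, with relation to a pre-existing condition as an attribute. It is then classified for seriousness and reaches the medical monitor.
3. State in Primary Outcome Measures that (b) counts any bleeding, infection, pneumothorax or arrhythmia regardless of attribution, with attribution reported alongside. This matches the present wording, which sets no limit by cause, and closes the route by which an omission could reach the primary outcome.

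The cost is one deleted clause, one added sentence and one eCRF field. A few more events may need recording and review, and the freedom rate may look less favourable. No clinical management changes.

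### The arrhythmia row presumes device causality from one switch-off, which makes the reported device-relatedness of arrhythmias unreliable but leaves the primary count of any arrhythmia unchanged

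*Combined protocol and SAP*

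**What the plan says.** The arrhythmia row of the table under Risks and Risk Mitigations Strategy (in Risk Assessment and Adverse Events) has the stimulator turned off when an arrhythmia occurs. Three sentences follow:

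- Resolution: "If this resolves the arrhythmia, then it will be noted that the device likely caused the arrhythmia".
- Persistence: "If the arrhythmia persists despite the device being turned off, then it is unlikely that the device is the cause of the arrhythmia".
- Lead: "If there is suspicion that the lead itself, even while turned off, is responsible for an arrhythmia, then the lead will be removed".

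The row gives no observation window. It makes no allowance for spontaneous resolution or for treatment given at the same time, and it does not ask whether stimulation was running at onset. Yet Study Device and Technique Description (Postoperative) lets patients stop stimulation whenever it causes discomfort.

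Relatedness is defined twice. Definition of Adverse Events has "Device and procedure relationships (unrelated, possibly related, or related". The text introducing the risk table has "AEs will be collected and classified as device-related, procedure-related or unrelated".

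Two parties handle attribution. Under Medical Monitor: "The medical monitor will assess all AEs captured by the study coordinator(s". Under Monitoring, the site monitor checks that "AEs have been reviewed, attribution has been assigned and signed by investigator in a timely manner". The primary safety outcome is "Freedom from bleeding, infection, pneumothorax, arrhythmias".

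**The concern.** The row reads a one-time switch-off as a causal test. Resolution does not separate a device effect from an arrhythmia that was about to stop or was being treated. Persistence does not clear the device, because an arrhythmia can continue after its trigger is gone. If the patient had already stopped stimulation before onset, the test cannot be performed and the row offers no other route to an attribution.

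The study has one arm and no control, so no comparison would correct these errors. At stake is the statement of how many arrhythmias were device-related, in a study whose stated purpose includes the safety of an electrical lead in the chest. The definition of an unanticipated adverse device effect also turns on a link to the device, and the Reports section attaches a 10-working-day deadline to it. That route is narrower than it looks: the event must be serious, and its nature, severity or frequency must go beyond what the plan already lists. Arrhythmia is listed.

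**Working it through.** The plan has no figure to reproduce. It gives no arrhythmia rate, and the sample size of 10 has no calculation behind it. The check is therefore a comparison of texts, followed by an illustration under assumed rates.

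**Mapping the row to the relatedness classifications**

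| Outcome in the arrhythmia row | Term used | Instruction to record? | Level in Definition of Adverse Events | Class in the risk-table introduction |
|---|---|---|---|---|
| Stops after switch-off | likely | yes | none matches | none matches |
| Persists after switch-off | unlikely | no | none matches | none matches |
| Lead suspected while off | no term | no (lead removal only) | none given | none given |
| Stimulation already off at onset | not addressed | no | none given | none given |

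The two classifications also differ from each other. One grades strength of relation. The other sorts events by source and has no intermediate level.

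**Size of one reclassified subject.** In the full study, 1/10 = 10 percentage points. In the interim progress report on the first 5 subjects, 1/5 = 20 percentage points.

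**Illustration: background arrhythmias noted as device-caused.** Let p be the proportion of subjects with an arrhythmia unrelated to the device, and s the share of those that stop after switch-off, by chance or with treatment. Both are assumptions.

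- At least one background arrhythmia in 10 subjects: 1 − (1 − p)^10. For p = 10%, 1 − 0.9^10 = 65%. For p = 30%, 1 − 0.7^10 = 97%.
- Expected number of false notes: 10ps. For p = 5–30% and s = 10–75%, this runs from 10 × 0.05 × 0.10 = 0.05 to 10 × 0.30 × 0.75 = 2.25.
- At least one false note: 1 − (1 − ps)^10. Over the same ranges it is 4.9% to 92%. At p = 20%, s = 50%, it is 1 − 0.9^10 = 65%.

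**Illustration: what the switch-off result tells us.** Let π be the share of arrhythmias that are device-triggered and q the share of those that persist after switch-off. Both are again assumptions.

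- P(device | stops) = π(1 − q) / [π(1 − q) + (1 − π)s]
- P(device | persists) = πq / [πq + (1 − π)(1 − s)]

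At π = 10%, s = 50%, q = 25%:

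- stops: 0.075 / (0.075 + 0.45) = 14%
- persists: 0.025 / (0.025 + 0.45) = 5.3%

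So the result moves the probability from 10% to 14% or to 5.3%. With s and q at these values, *likely* is correct (above 50%) only if 0.75π > 0.5(1 − π), that is π > 40%. If s = 1 − q, for example both 50%, both results leave the probability at π and the test is uninformative.

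Over π = 5–30%, s = 10–75% and q = 0–50%, P(device | stops) runs from 3.4% to 81% and P(device | persists) from 0% to 46%. The *unlikely* label is often right on average, but a fraction q of device-triggered arrhythmias would still attract it.

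**The case against.** The best defence is that these sentences sit in a risk-mitigation column, use hedged words, and do not settle attribution. The investigator assigns and signs it. An independent medical monitor, set up to keep classification consistent and accurate, assesses every adverse event, and nothing binds that monitor to the row. With ten subjects on cardiac monitors after surgery and results described as case reports, each arrhythmia can be narrated individually. Most of this stands: the row is a presumption, not a final ruling. But those who must attribute have no criteria for departing from it, no required data on onset or stimulation state, and no statement of whose view prevails.

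Four stronger readings are tempting, and the documents do not support them:

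- *The primary safety result is corrupted.* The primary outcome is not limited to device-related arrhythmias, so attribution cannot change its count.
- *Arrhythmias caused by the lead are labelled unlikely device-related, in contradiction to the next sentence.* The row begins by turning off the stimulator and then treats the lead as a separate possible cause. That reads as an exception. What it lacks is an attribution category.
- *Every persisting device-triggered arrhythmia is recorded as unlikely related.* Only the resolution sentence contains an instruction to record.
- *The trial cannot report device-related arrhythmias at all.* It can describe each case. What it cannot do under this wording is classify them reliably.

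**Conclusion.** The concern holds as a flaw in a stated attribution rule. Following the row would note a self-limiting or treated arrhythmia as probably device-caused, and would lean towards clearing the device when a stimulation-triggered arrhythmia persists. Its terms cannot be placed on either relatedness classification. The consequence is limited to reported device-relatedness (10 percentage points per subject at 10 subjects, 20 at the 5-subject interim report) and to device-effect reporting that depends on it.

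How many subjects would be misattributed is unknown. The illustrative range of 0.05 to 2.25 false device notes rests wholly on assumed rates and on the note being carried through to the final attribution, which the documents do not say. The logical defect needs no rate. The resolution half is the weaker of the two. The persistence half is often right on average, but not as a rule for the individual case.

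**What to change.** Leave every care step in the row as it is and replace only the two attribution sentences:

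1. State that response to switch-off is one input, and that neither resolution nor persistence alone determines relatedness.
2. For each arrhythmia, record onset time, stimulation state at onset, whether the lead was in or out, time from switch-off to resolution, and any treatment given in that interval.
3. Reconcile the two relatedness classifications into one scale. Grade relatedness to stimulation and to presence of the lead separately on it.
4. State that the independent medical monitor's classification is final.

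I would not substitute a default in the other direction, such as grading every arrhythmia with the lead in place as at least possibly related. Under an assumed 10–30% background rate, 1 to 3 unrelated arrhythmias are expected in 10 subjects, and most could receive that grade by default.

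The cost is a wording change and a few eCRF fields. Cardiac monitoring during the stay is already standard care. Some events may move between categories, which could make the device safety figure slightly less favourable.
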